Randomization Process: The randomization process will be performed using a random number table and recorded separately into sealed envelopes. These envelopes will be randomly placed into patient folders. After the informed consent process, facilitator will open the randomization envelope. The patient will not know what group they have been randomized to, only the facilitator and study staff will know which group the patient is in. . .

Facilitators: The facilitators are an integral part of the study team. They have all of the proper training (IRB, HIPPA, NIH, etc.) to work with patients in health care and research settings. The Facilitators will be responsible for administering the surveys to collect the data on emotional well-being. The facilitators will also be familiarized with administering the *Transform-10* Program. The facilitators are supervised by the attending orthopaedic trauma physician ([name] or [name]), [name], and a clinical psychologist, [name]. [name], Drs. [name] and [name], and [name] will also serve as mentors for the facilitators as questions arise regarding the implementation of the *Transform-10* Program. The facilitators will make daily rounds with the trauma physician and other daily visits during the patients' hospital stay to ensure they are adhering to their treatment plan and to clarify any details about the patient's injury or treatment plan. The facilitators will serve as liaisons between the hospital staff, physician, clinic staff, and discharge planner. These individuals will be in daily communication with the study team, physician, and/or other hospital personnel to ensure patient safety and that the patients' medical questions are presented back to the attending physicians. Daily monitoring of facilitators by the attending orthopaedic trauma physician and study team will occur via morning conference prior to meeting with patients and a debriefing with the study coordinator at the conclusion of each day.

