Study Groups: The ICare will be compared to UsCare. This choice of comparators was made for several reasons. UsCare for orthopedic trauma involves surgical intervention, acute care therapies, post-acute rehabilitation and follow-up clinic visits after discharge. Psychosocial support and resources are commonly provided after discharge, but only if needed. ICare provides the simultaneous provision of psychosocial support and medical care beginning at admission to the trauma service. After hospital discharge Both study groups will be asked to come to the Human Dynamics Laboratory/Sports Performance Center at the Orthopaedic and Sports Medicine Institute (this building is where they will have follow up visits with their physician) about an hour early to complete the functional assessments and questionnaires. For the ICare group, the remaining steps for the *Transform-10* Program will be reviewed within this time. After the assessments and questionnaires, the participant will be escorted to the clinics on the second floor to see the physician.

1. Usual Care (UsCare). Post-operative care is based on widely-accepted recommendations⁸ and on the current understanding of injury treatment. The key components of the care system include medical stabilization, injury repair, discharge planning and physical rehabilitation. Usual Care includes radiographic imaging and administration of pain medication and antibiotics, skin care and range of motion of the injured area. The attending physician visits with the patient a minimum of once per day and the nursing staff attends to patient care approximately once every four hours. Upon admission to acute care, the attending physician (*[name] or [name]*) will introduce the team to the patient and explain the purpose and activities involved in the medical approach. The patient will have the ability to ask questions and express concerns. Each patient will be assigned a Facilitator who will have contact with the patient. All medical processes will proceed under the guidelines of Usual Care. The Facilitator will visit the patient when the Attending Physician performs rounds only. If applicable, the Clinical Psychologist (*[name]/ Postdoctoral Fellow*) will review patient concerns and issues as presented to him by the Attending Physician. The initial measures will be obtained in the hospital setting, and follow-up measures will be collected in the typical outpatient times out Protocol

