The prevalence of medical complications, rehospitalizations and comorbid disease will be captured in two ways: 1) using data extraction methods from the electronic medical records, and 2) directly from patients during their follow-up visits in the outpatient clinics. The number of readmissions (and length of the readmissions), reasons for readmissions, the number and type of complications will be collected. The onset of new comorbid diseases, with particular emphasis on psychological illnesses, will also be collected using these following tools that have been validated for use in the trauma population:

- **The Posttraumatic Stress Disorder (PTSD) Checklist** will be administered to measure posttraumatic stress levels. The PTSD Checklist has high temporal and internal consistency and high content validity.⁴⁹
- **The Beck Depression Inventory-II**²⁹ is a broadly-applicable, clinically relevant psychometric instrument with high reliability and consistency.⁵⁰ BDI-II has high capacity to discriminate depressed and non-depressed people.⁵⁰
- **The State-Trait Anxiety Inventory (STAI)** will be used to measure state anxiety (anxiety about an event) and trait anxiety (anxiety level as a personal characteristic). Internal consistency ranges from 0.86 to 0.95, with considerable evidence of the construct and concurrent validity of STAI-II.⁵¹ STAI values correlate with negative outlook of self and their current experience after traumatic injury.⁵²
- **Pain-Related Fear:** Kinesiophobia is the psycho-social, somatosensory neuronal feedback, manifestation of fear of movement due a belief it will induce pain or injury.^{53,54} To assess the pain-related fear in orthopaedic trauma the Tampa Scale of Kinesiophobia-11 (TSK-11) will be used ($\alpha=0.79$, $ICC=0.81$).⁵⁴

6. Research Quality: Exit Survey about patient perceptions of research and subject interactions.

We hypothesize that the Integrated Care group (with the Transform 10 Program) will have fewer rehospitalizations, medical complications and comorbid disease will be present in the Integrated Care group compared to Usual Care.

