Complications and Safety Events: A structured safety monitoring system will assure real-time participant care and unbiased monitoring of safety. A summary of complications and safety events will be reported by the Study Coordinator. For ongoing participant safety, events will be assessed by the PI, physician, and Co-investigators to determine if they are Serious, Unexpected or On-site. If so, an event evaluation form will be completed that will include a description of the event, a classification of seriousness, assessment of potential relationship to the study, assessment of need for change in the consent or the study activities, a summary of known prior health issues, event outcome and a classification of the main organ system involved. Participants will be instructed to talk with the study team about any discomforts that occur during the study whether they believe the discomfort is related to the study or not. All patients will be monitored 24 hours a day, 7 days a week while in the acute care service. Should any abnormal physiological response occur (e.g., abnormal heart rhythm, dizziness) the Attending Physician (*[name]*) will be alerted to mobilize the appropriate safety response.

Statistical Analysis: The Statistical package for the Social Sciences (SPSS, v 22.0; Chicago, IL) will be used for analysis. Descriptive statistics will be calculated on

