Stress: Patients will not experience greater risks if randomized to one care approach over the other. The measures that will be conducted during the study include PROMIS instruments, surveys and brief functional tests (handgrip strength, ROM, LEGS functional measures). The risks to performing these patient reported outcomes and functional tests are very low. Although a minimal risk, completing surveys may cause stress to some participants who may believe that they are not providing correct answers to the study team. The survey questions have a very low psychological risk if participants are upset by questions that ask them to think about their own poor health or problems that are disturbing. Should a patient present, answer, or score in particular negative manner on the psychological measures we have implemented, a Distress Referral Protocol for the patient's safety. This protocol states that patients scoring one standard deviation above the normative range for this patient population will receive further evaluation by the clinical psychology service.

Physical Discomfort: Potential minor discomforts of some of the functional tests can include transient muscle soreness for all patients, whether in the study or not. Muscle soreness may occur when participants begin moving again after injury. This symptom is common following unaccustomed physical activity, and the duration of this soreness is generally up to 48 hours after the activity.⁵⁹ The study team members will explain this potential risk to all participants to minimize this stressor.

Protections Against Discomforts and Risks:

Consent and Confidentiality: Potential participants will be asked to read the informed consent form and to ask questions. The form will be written in simple, easy-to-understand language. We require the coordinator to review all key aspects of the study verbally. They will then question potential participants to ascertain whether they have understood the information. A copy of the signed and dated consent form will be given to participants, and the original document will be placed in subjects' individual study files, which will be stored in a locked, secure location in the OSMI (room 1135).

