The Psychology Service will consist of [name] assisted by graduate students, interns, and/or postdoctoral fellows in the Department of Clinical and Health Psychology at UF. Trainees on that service will be directly supervised by [name]. Those services will include a formal clinical interview, development of a diagnostic conceptualization, development of a treatment plan, and provision of treatment designed to reduce the patient's distress and improve coping. Treatment will usually consist of cognitive-behavioral interventions with strong scientific support for their efficacy. The BDI and STAI may be re-administered periodically to assess level of improvement after treatment has been initiated. Psychological treatment visits can be reduced in frequency or stopped following sufficient decrease in patient symptom scores and perceived distress.

Data Safety and Monitoring Plan.

A Data and Safety Monitoring Plan (DSMP) will be implemented to ensure the safety of all participants involved in the study and to ensure the validity and integrity of the data. The PI with the advice and assistance of the study team will monitor all aspects of safety. The Study Coordinator will meet monthly with the PI to review all Serious, Unexpected and On-site adverse events. Within 24 hours of initial confirmation, the PI will complete an Event notification and Evaluation form for all Serious, Unexpected and On-site adverse events which will be reviewed by the IRB. Non-serious event tracking will be monitored using the Health Events Questionnaire data collected following the running protocol. A summary of these non-serious events will be reported to the PI and IRB. A structured safety monitoring system will be established in order to both assure real-time participant care and unbiased monitoring of adverse outcomes. For ongoing participant safety, events will be assessed by the PI, physician, and Co-investigators to determine if they are Serious, Unexpected or On-site. If so, an event evaluation form will be completed that will include a description of the event, a classification of seriousness, assessment of potential relationship to the study, assessment of need for change in the consent or the study activities, a summary of known prior health issues, event outcome and a classification of the main organ system involved. The classification of potential relationship to the intervention is as follows.

Definite - Temporal pattern + Known or expected AE response pattern

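### The safety plan's only named tool for non-serious events is a questionnaire the trial never defines, tied to a running protocol it does not have, so the promised event summary has no usable source

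*Protocol*

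**What the plan says.** **Safety plan.** Under section 7, Data Safety and Monitoring Plan, the protocol states: "Non-serious event tracking will be monitored using the Health Events Questionnaire data collected following the running protocol". A summary of these events then goes to the PI and the IRB. The same paragraph commits the study to unbiased monitoring of adverse outcomes.

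**Measures.** Section 7, Stress, describes what will be done to participants: "The measures that will be conducted during the study include PROMIS instruments, surveys and brief functional tests", the functional tests being handgrip, range of motion and the Lower Extremity Gain Scale.

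**Complications.** Section 6, under Medical Complications, Rehospitalizations and Comorbid Disease, gives two routes: "using data extraction methods from the electronic medical records" and "directly from patients during their follow-up visits in the outpatient clinics". Readmissions are recorded with their length and reasons, and "the number and type of complications will be collected". Neither route is described differently by arm.

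**Discomforts.** Section 6, Complications and Safety Events, adds: "Participants will be instructed to talk with the study team about any discomforts that occur during the study".

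**Facilitator contact.** For Usual Care: "The Facilitator will visit the patient when the Attending Physician performs rounds only". Integrated Care adds the Transform-10 sessions of roughly 10 to 30 minutes in hospital, with remaining steps reviewed at follow-up visits. The Facilitators paragraph says, without naming an arm: "The facilitators will make daily rounds with the trauma physician and other daily visits".

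The SAP does not mention safety events or how they are collected.

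**The concern.** The sentence in the safety plan is the only place where the protocol assigns a data source to non-serious events. If that source does not exist in this trial, the study team has no defined way to produce the summary it owes, and two people compiling it could count different things.

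Equal capture matters here for two reasons. First, the arms differ in how much time a patient spends with a facilitator, so a route that depends on the patient speaking up may not work equally in both. Second, only Integrated Care includes a structured exercise program before supervised physical therapy begins. Minor physical events are therefore something a reader would want to compare between arms. A standard questionnaire would be the natural safeguard, and it is the element left undefined.

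**Working it through.** The plan gives no event rate or capture rate, so there is no figure to reproduce. The check is a comparison of texts.

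1. **Is the questionnaire defined anywhere?** It is named once, in the Data Safety and Monitoring Plan. It is absent from Data collection and Measurements and the numbered outcome headings that follow (functional quality of life, functional ability, emotional well-being, complications, research quality), and from the list of measures in section 7. No items, timing, mode or administrator are given.

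2. **Is there a running protocol?** No running test or intervention appears in either document. The functional measures are handgrip, the Lower Extremity Gain Scale and range of motion. The wording looks carried over from another study.

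3. **Does another listed instrument do the job?** The tools listed with complications are the PTSD Checklist, the BDI-II, the STAI and the TSK-11. As the protocol describes them, they measure psychological state or fear of movement. The exit survey concerns perceptions of the research. None is described as a health-event form.

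4. **Which events still have a route?**

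| Type of event | Stated route | Same in both arms? | Standard form named? |
|---|---|---|---|
| Readmissions, and complications in the medical record | Record extraction | Yes, as written | Extraction; no form needed from the patient |
| Complications known only to the patient | Collected from patients at follow-up visits | Yes, as written | No |
| Minor non-serious events outside both | Undefined questionnaire; otherwise the patient raises it | Same instruction, unequal contact | No |

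5. **How unequal is contact?** In hospital, Usual Care patients see the facilitator at physician rounds, which occur at least daily; Integrated Care patients have the Transform-10 sessions as well. After discharge, both arms are asked to arrive about an hour early for the assessments and questionnaires, and Integrated Care patients also review program steps in that time. Round-the-clock monitoring applies to everyone, but only in acute care, while follow-up runs to 12 months. The general statement about other daily visits has to be reconciled with the rounds-only rule for Usual Care before the difference can be described exactly.

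6. **Direction and size.** More contact gives more occasions to mention a minor event, so any difference would probably mean fuller reporting in Integrated Care. The documents give no capture rates, and any percentage-point figure would rest wholly on assumed ones. The size is unknown.

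**The case against.** The strongest reply is that this is a stray phrase with little consequence. The word running might mean ongoing, and the list of measures mentions surveys without naming them all. The Aim 3 outcomes have their own sources, and nothing links the questionnaire to that comparison. Visit data go into REDCap forms with a checklist and weekly review. All patients are told to report discomforts, all are monitored as inpatients, and Usual Care patients also have an assigned facilitator. The procedures are described as very low risk. Any under-reporting would fall in the arm that receives no added intervention, so a signal caused by the program would be the better observed one.

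Much of this stands. Aim 3 is not shown to depend on the faulty source, the imbalance in contact is partial, and its effect on reporting is conjecture. It is also fair to call the questionnaire undefined here rather than impossible.

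Two things remain. Reading running as ongoing still leaves a questionnaire with no content, schedule or administrator. And REDCap review can check only forms that exist; no health-event form is named for the safety summary or for collecting complications from patients at visits.

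**Conclusion.** The point holds in a limited form. The stated method for tracking non-serious events cannot be carried out as written, and the summary for the PI and the IRB has no usable source. The exposed part is minor non-serious events that are not counted as complications, do not reach the record and are not asked about at visits, together with the unstandardised patient-report route. This rests on the text alone and needs no numerical assumption.

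A reader might infer that event capture as a whole falls back on spontaneous reports, and that the Aim 3 comparison is therefore biased. The documents do not support that. Section 6 plans record extraction and collection at visits in both arms, and the questionnaire sentence belongs to the safety plan only. A reader might also attach a number to the bias, but neither document supplies the capture rates needed.

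Fuller reporting of minor events in Integrated Care remains plausible. It is an inference from planned contact, its size is unknown, and it would work against the hypothesis of fewer events in that arm.

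**What to change.** Replace the sentence in the Data Safety and Monitoring Plan with: *The same fixed set of health-event questions will be asked in both arms, in REDCap, at weeks 2, 6 and 12 and months 6 and 12, and will be the source of the non-serious-event summary.* Add the form to the measures in section 6, and use it for the complications collected from patients at follow-up visits, alongside the planned record extraction. Remove the reference to a running protocol.

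Because the research team knows the allocation, completion by the patient, or questioning by staff unaware of the arm where feasible, would be preferable. The protocol already allows surveys to be emailed. The two descriptions of facilitator visits should be reconciled at the same time.

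Cost: one corrected sentence, one short form, and about a minute more per visit. Over five follow-up visits that is 5 × 1 = about 5 minutes per patient. The minute is an estimate, not a figure from the documents.

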Probable - Temporal pattern + Known or expected AE response pattern + Could not be explained by participant's clinical state

Possible - Temporal pattern + Known or expected AE response pattern + Could have been produced by a number of other factors

Unknown - Relationship for which no evaluation can be made.

Not related - AE for which sufficient information exists to indicate that the cause is unrelated to the study intervention

The study PI and Co-investigators will notify the IRB of any serious adverse events that result in death or additional medical care within 24 hrs. The PI, [name], can be reached at [contact].

8. Possible Benefits:

There is no direct benefit to any of the patients whose data are used in this study. However, there are indirect benefits of the analysis of these data. The study team completed research to determine what outcomes are important to patients who are receiving care after orthopedic surgery. Identification of common patient experiences and concerns helped to shape our research questions on the outcomes important to patients and caregivers. This is significant because we can effect meaningful change in how patients are managed during their hospital stay and beyond.

Analyze the risk-benefit ratio: This study poses relatively low risk to individuals. It poses a low risk of breach of PHI. The possibility of identifying processes that can improve patient care and safety is very helpful for patients, families and providers. These data can be used to help patients and providers in the future incorporate processes that can improve patient experience and outcomes after orthopedic trauma injury. The risk-benefit ratio is acceptable.

Conflict of Interest

The study team has no conflict of interest to report.

Sources of funding:

This project has received support from the Foundation for Physical Medicine & Rehabilitation, the National Athletic Trainers' Association and the W. Martin Smith Interdisciplinary Patient Quality and Safety Award.

References

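### In the adverse-event relationship scale, Definite requires less than Probable or Possible, so an event can qualify for more than one grade

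*Protocol*

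**What the plan says.** The scale closes the Data Safety and Monitoring Plan in section 7 of the Protocol. It has five lines:

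- The strongest grade lists two elements: "Definite - Temporal pattern + Known or expected AE response pattern".
- The next grade down repeats both and adds a third: "Probable - Temporal pattern + Known or expected AE response pattern + Could not be explained by". The quote stops short of its object, which is the clinical state of the patient.
- The weakest of the three grades also repeats both, with a different addition: "Possible - Temporal pattern + Known or expected AE response pattern + Could have been produced by a number of other factors".
- A fourth category is kept for events that cannot be judged: "Unknown - Relationship for which no evaluation can be made".
- The fifth asks for positive evidence of another cause: "Not related - AE for which sufficient information exists to indicate that the cause is unrelated to the study intervention".

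The scale follows directly on the list of items for the event evaluation form, one of which is the event's potential relationship to the study. On timing and scope, the same section says: "Within 24 hours of initial confirmation, the PI will complete an Event notification and Evaluation form for all Serious, Unexpected and On-site adverse events". That form goes to the IRB for review. A later sentence there, and the paragraph on complications and safety events in section 6, put the scope differently: "events will be assessed by the PI, physician, and Co-investigators to determine if they are Serious, Unexpected or On-site". Section 7 also sets a separate notice, under which the investigators "will notify the IRB of any serious adverse events that result in death or additional medical care within 24 hrs".

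Neither the Protocol nor the SAP gives an order of precedence among the grades, a rule of one grade per event, or a residual category.

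**The concern.** A causality scale should demand more evidence as the label gets stronger. Here the strongest label has the shortest list of requirements. The two considerations that would weaken a causal attribution, namely the patient's clinical state and other possible causes, appear only under the weaker labels. In hospitalised surgical trauma patients these are obvious alternative explanations.

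What is at stake is the grade entered on the event form. Two assessors could follow the text faithfully and grade the same event differently, or could enter Definite where a competing cause is plain. The assessors are the PI, physician and co-investigators, and section 6 says that the research and care teams know the allocation. Written criteria are thus one of the few safeguards on the consistency of the grade.

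**Working it through.** No figure in the plan is at issue, so the check is one of logic. Four criteria are taken from the wording of the scale:

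- A: temporal pattern
- B: known or expected response pattern
- C: not explained by the participant's clinical state
- D: could have been produced by other factors

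**Step 1, ordering.** As written, Definite = A and B; Probable = A and B and C; Possible = A and B and D. Adding a condition can only narrow a set, so Probable and Possible both lie inside Definite.

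**Step 2, overlap.** Take an event with both patterns (A and B true):

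| Explained by clinical state? | Other factors possible? | Grades met as written |
|---|---|---|
| No | No | Definite, Probable |
| No | Yes | Definite, Probable, Possible |
| Yes | Yes | Definite, Possible |
| Yes | No | Definite |

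Definite is met in every row. In the last row, where the clinical state explains the event, it is the only grade met.

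**Step 3, can a tacit rule rescue the text?** If the strongest grade met is taken, every such event is Definite, and Probable and Possible are never used. If Definite is read as what remains after Probable and Possible, only the last row remains, and those are events that the clinical state could explain. If clinical state counts as one of the other factors, the last row cannot occur and residual Definite is empty. Neither rule gives a usable scale.

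**Step 4, an example from the Protocol.** Section 7, under physical discomfort, says that functional tests may cause transient muscle soreness lasting up to about 48 hours. It adds that soreness also arises in patients outside the study when they start moving again. Soreness after a test thus has the timing, a known pattern and another possible cause. If it reached the form, it would meet both Possible and Definite.

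**Step 5, events without both patterns.** An event lacking A or B fails all three grades. Not related needs positive information that the cause lies elsewhere. Unknown is confined to relationships that cannot be evaluated. An event that was evaluated, lacks a pattern and is not shown to be unrelated is therefore not clearly placed.

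**Step 6, scope.** The documents do not define Unexpected. Assume that it means no known or expected pattern (B false). If an event must meet all three descriptors to get the form, no form event can meet Definite, Probable or Possible, and only the placement question in step 5 matters. If any one descriptor is enough, the ordering defect reaches Serious or On-site events that fit a known pattern, and step 5 reaches the Unexpected ones.

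**The case against.** The strongest reply is that the grade drives nothing. The 24-hour form is triggered by the type of event, and the 24-hour IRB notice by a serious event leading to death or further care. No stopping rule or analysis refers to the grade. The form also carries a description, prior health issues, the outcome and a separate judgement on whether consent or study activities should change, so the IRB does not rely on the label alone. On one reading of the scope (step 6), the ordering defect touches no form event. All of this stands, and it limits the point to a minor one. It does not make the definitions coherent.

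A second reply is that Unknown can take the unassigned events: where support is lacking and there is too little information to call the event unrelated, an assessor may fairly say that no evaluation is possible. This also stands in part. A reader might infer that some events cannot be coded at all, but the text does not support that. It supports only that their category is left to an unwritten convention.

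A third reply is that a further criterion may have dropped off the Definite line when the document was converted to text. The line reads as complete and nothing points to a loss, but this cannot be wholly excluded. A check against the PDF would settle it. The placement question would remain either way, since Probable and Possible still require both patterns.

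**Conclusion.** The ordering defect holds on the wording as printed: Definite has the lowest bar of the three grades, and every Probable or Possible event also satisfies it. The unclear placement of events that lack a pattern is a real but softer point.

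The severity is minor. How often events would be misgraded cannot be estimated from the documents.

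Two further inferences should be resisted. One is that the defect compromises IRB reporting or the trial's comparisons. The documents do not support this, because no trigger or planned analysis uses the grade. The other is that correcting the scale cannot move any event between related and unrelated. That depends on where the sponsor places the events lacking a pattern: put under Possible they would count as related, put under Unknown they would not.

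The conclusion rests on two readings: that the scale is the one used for the relationship item on the form, which it directly follows, and that the notification form and the event evaluation form are the same document. The remarks on scope also rest on the assumed meaning of Unexpected.

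**What to change.** Reconcile the definitions so that the grades are ordered and each event receives exactly one. The documents do not say what Definite was meant to require, so the following wording is only an example:

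- **Definite:** both patterns, not explained by clinical state, and not plausibly produced by other factors.
- **Probable:** both patterns, not explained by clinical state, but other factors not excluded.
- **Possible:** both patterns, and could have been produced by clinical state or other factors.
- **Rule:** assign the first grade met in that order.

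Applied to the rows of the table in order, this gives Definite, Probable, Possible, Possible. The rule is needed: without it, the second row would meet both Probable and Possible.

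In addition:

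- Name the category for events that lack a pattern and are not shown to be unrelated, for example by widening Unknown to cover them.
- Use either *and* or *or* throughout for the events that receive the form, and define Unexpected.
- Re-review any events already coded.

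The cost is a few words in the monitoring plan and on the form, plus a short re-review if events have been coded. Sample size, visits and analyses do not change.
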